8.4.7 Events of Special Interest

Any incidental radiographic findings discovered on PET-CT imaging will be reported to a study subject no later than 7 days after the PI first learns of the result.

8.4.8 Reporting of Pregnancy

If the serum or urinary beta-HCG result of a female participant is positive at the time of screening, the individual will be informed of this result and excluded from the study. All female subjects will receive pregnancy testing prior to radiation exposure. Should a subject find out that she became pregnant while participating in this study, she should notify the team immediately. The team will provide counseling on the risks of radiation to the fetus. The investigators will report the pregnancy to the IRB and NHLBI Clinical Director at the Continuing Review as a reason subject was withdrawn early from the study

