x² = A plasma or urinary HCG in female subjects who are of child-bearing age will be collected within 7 days of study participation. While on study women of child-bearing age will have pregnancy test at each visit unless test has been performed within 24 hours of study visit

x³ = Patient may not use platelet inhibitors (e.g. clopidogrel) within 7 days or systemic anticoagulants (e.g. warfarin, enoxaparin, or DOAC) within 14 days of bronchoscopy.

X⁴ = Tuberculin skin test (TST) to placed prior to screening labs. A second TST may be completed per PI or designee if needed to confirm negative results one to three weeks after the first TST.

** = Bronchoscopy for visit 4 and visit 6 will be performed within 2 days after the PET-CT

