- **Reproductive Risks:** Since PET-CT scans involve exposure to radiation which can lead to teratogenic effects to a fetus. For this reason, women of child-bearing age will undergo pregnancy testing prior to PET-CT scan and be excluded from the study if testing is found to be positive.

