8.4.2 Definition of Serious Adverse Events (SAE)

An adverse event (AE) or suspected adverse reaction is considered "serious" if, in the view of either the investigator or sponsor, it results in any of the following outcomes: death, a life-threatening adverse event, inpatient hospitalization or prolongation of existing hospitalization, a persistent or significant incapacity or substantial disruption of the ability to conduct normal life functions, or a congenital anomaly/birth defect. Important medical events that may not result in death, be life-threatening, or require hospitalization may be considered serious when, based upon appropriate medical judgment, they may jeopardize the participant and may require medical or surgical intervention to prevent one of the outcomes listed in this definition. Examples of such medical events include allergic bronchospasm requiring intensive treatment in an emergency room or at home, blood dyscrasias or convulsions that do not result in inpatient hospitalization, or the development of drug dependency or drug abuse.

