8.4.4 Time Period and Frequency for Event Assessment and Follow-Up

The occurrence of an adverse event (AE) or serious adverse event (SAE) may come to the attention of study personnel during study visits and interviews of a study participant presenting for medical care, or upon review by a study monitor.

All AEs including clinically significant laboratory tests, local and systemic reactions not meeting the criteria for SAEs will be captured on the appropriate case report form (CRF). Information to be collected includes event description, time of onset, clinician’s assessment of severity, relationship to study product/research procedure (assessed only by those with the training and authority to make a diagnosis), and time of resolution/stabilization of the event. All AEs occurring while on study must be documented appropriately regardless of relationship. All AEs will be followed to adequate resolution.

Any medical condition that is present at the time that the participant is screened will be considered as baseline and not reported as an AE. However, if the study participant's condition deteriorates at any time during the study, it will be recorded as an AE.

Changes in the severity of an AE will be documented to allow an assessment of the duration of the event at each level of severity to be performed. AEs characterized as intermittent require documentation of onset and duration of each episode.

The principal investigator will record all reportable events with start dates occurring any time after informed consent is obtained until 7 (for non-serious AEs) or 30 days (for SAEs) after the last day of study research procedure or until resolution or stabilization of an SAE whichever comes later. At each study visit, the investigator will inquire about the occurrence of AE/SAEs since the last visit. Events will be followed for outcome information until resolution or stabilization via in person, telephone and or e-mail.

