8.4.6 Serious Adverse Event Reporting

The study investigator will report to the sponsor any serious adverse event, whether or not considered study intervention related, including those listed in the protocol and must include an assessment of whether there is a reasonable possibility that the study intervention caused the event.

All serious adverse events (SAEs) will be followed until satisfactory resolution or until the investigator deems the event to be chronic or the participant is stable.

The study sponsor will be responsible for notifying the Food and Drug Administration (FDA) of any unexpected fatal or life-threatening suspected adverse reaction as soon as possible, but in no case later than 7 calendar days after the sponsor's initial receipt of the information. In addition, the sponsor must notify FDA and all participating investigators in an Investigational New Drug (IND) safety report of potential serious risks, from clinical trials or any other source, as soon as possible, but in no case later than 15 calendar days after the sponsor determines that the information qualifies for reporting.

All SAEs will be reported to the DSMB at the time of review. However, if an SAE is considered, unexpected and related to the intervention, the study investigator will notify the DSMB of the event within 48 hours.

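### Section 8.4.8 reports an on-study pregnancy only at Continuing Review, with no prompt sponsor report and no follow-up to outcome, so a birth defect counts as an SAE only if the site comes to hear of it

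*Combined protocol and SAP*

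**What the plan says.** **The pregnancy rule.** Under 8.4.8 a participant who finds she is pregnant is to tell the team at once, and the team counsels her on radiation risk to the fetus. Then: "The investigators will report the pregnancy to the IRB and NHLBI Clinical Director at the Continuing Review as a reason subject was withdrawn early". The section names no other recipient, sets no day limit, and does not mention how the pregnancy ends.

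**The hazard and the outcome.** Section 2.3.1 says that PET-CT involves "exposure to radiation which can lead to teratogenic effects to a fetus". The list of serious outcomes in 8.4.2 ends with "or a congenital anomaly/birth defect".

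**The general SAE route.** Section 8.4.6 states: "The study investigator will report to the sponsor any serious adverse event, whether or not considered study intervention related", and "All SAEs will be reported to the DSMB at the time of review". Section 8.4.4 has the principal investigator record events "with start dates occurring any time after informed consent is obtained until 7 (for non-serious AEs) or 30 days (for SAEs") after the last research procedure, "or until resolution or stabilization of an SAE whichever comes later".

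**Controls on study.** A footnote to the schedule in 1.3 says that "women of child-bearing age will have pregnancy test at each visit unless test has been performed within 24 hours of study visit". Section 7.1 lists a positive test as a reason to discontinue. Section 7.2 puts the reason for withdrawal on the CRF. Section 8.3 provides a web diary for self-assessed adverse events, reviewed at each visit.

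**The concern.** The protocol recognises a fetal hazard and classes the resulting harm as serious. Yet it treats the pregnancy itself as a withdrawal statistic. A site that followed 8.4.8 to the letter would counsel the woman, withdraw her, and list the withdrawal at the next review. It would have no planned step for learning how the pregnancy ended. The sponsor, which holds the FDA reporting duties in 8.4.6, would hear of an abnormal outcome only if news happened to reach the site.

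The protocol sets clocks for other matters: 7 days to tell a participant of an incidental imaging finding (8.4.7), 7 days to tell the sponsor that an AE is more frequent than expected (8.4.5), and 48 hours to notify the DSMB of an unexpected related SAE (8.4.6). Pregnancy has none. What is at stake is safety ascertainment, not the estimates or tests of any endpoint.

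**Working it through.** The plan states no figure to reproduce. The main check is to see whether another section supplies what 8.4.8 omits.

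- **7.1 and 7.2:** the positive test leads to discontinuation and the reason goes on the CRF. This makes a record, but starts no clock and no follow-up.
- **8.4.1 and 8.4.5:** an AE is an untoward medical occurrence, and pregnancy is not listed as one. Even if it were handled as an AE, 8.4.5 sends AEs to the sponsor only at continuing review and in the FDA annual report.
- **8.4.4 and 8.4.6:** following events to resolution applies to events already recorded. An uncomplicated pregnancy is not one.
- **8.5:** the unanticipated-problem route goes to the IRB and needs all three criteria to be met.
- **1.3 and 8.3:** AE review and the diary operate while the woman is on study. They do not reach to birth.

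None supplies a prompt sponsor report or follow-up to outcome.

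**Illustrative timing.** From the schedule, on nominal days: scans on days -7, 4 and 20; tests on days -7, 0, 4, 5, 20 and 21, where the day 5 and day 21 tests may be skipped if one was done within 24 hours. Assumed, because the documents do not say: hCG turns positive 8 to 14 days after conception, birth comes 266 days after conception, and the review interval is 6 or 12 months. Withdrawal is taken to occur at the first positive test. If no test remains, awareness is on day 30, or when hCG turns positive if that is later.

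1. *Exposure.* Conceptions from day -20 to day 20 can meet a scan, and at most two: 2 × 0.9 = 1.8 rem to the participant. The documents give no fetal dose, so no fetal risk is estimated.
2. *Detection after conception.* Minimum 8 days (conception day -8, lag 8, found day 0). Maximum 28 days (conception day -8, lag 14, found day 20), or 20 - (-9) = 29 days if the day 5 test is skipped. The visit windows in 1.3 lengthen this. With the day 4 and 5 visits two days early (the test on the second skipped) and the day 20 visit six days late, a pregnancy turning positive on day 3 is found on day 26: 26 - (-11) = 37 days. That table is broken in this copy, so this reading of the windows is itself an assumption.
3. *Latest report relative to birth.* At 12 months: lag + 365 - 266 = lag + 99, so 107 to 128 days after birth for lags of 8 to 29. At 6 months: lag + 183 - 266 = lag - 83, so 75 to 54 days before birth.
4. *From the nominal 30-day SAE limit to birth.* Conception + 266 - (last procedure + 30). Minimum 257 - 35 = 222 days (conception day -9, last procedure day 5). Maximum 286 - 51 = 235 days (conception day 20, last procedure day 21). If the positive-test visit counts as the last procedure, the minimum is 266 - 29 - 30 = 207.
5. *After the last test.* Day 30 is a telephone contact, so nothing tests for pregnancy after day 21. First positivity on day 22 or later means conception on days 14 to 20 (lag 8) or 8 to 20 (lag 14). Such a pregnancy met the third scan and surfaces only through the call or the woman's own notice. At lag 14, conceptions on days 17 to 20 are still not positive on day 30, since 17 + 14 = 31.

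Step 3 shows how far the result turns on an interval the documents do not give. Steps 4 and 5 show why on-study review cannot stand in for outcome follow-up.

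**The case against.** **Controls are already substantial.** They include contraception (5.1), exclusion for pregnancy (5.2), testing at visits and before radiation, discontinuation on a positive test, a thorax-only imaging field (2.3.3), and the duty to notify. The schedule also appears to place AE review at the day 30 call. All this stands, and it is why the expected frequency is very low. It does not tell anyone how a pregnancy ended.

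**The pregnancy does leave a record.** A reader might infer from 8.4.8 that it surfaces nowhere but Continuing Review. That goes too far: 7.2 puts the withdrawal reason on the CRF, where monitors may see it.

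**The 30-day limit.** A reader might infer that 8.4.4 excludes a birth defect from reporting even when the site knows of one. The text does not support that. The limit is tied to the event's start date and is followed by "or until resolution or stabilization of an SAE whichever comes later", and 8.4.6 sends any SAE to the sponsor. Explicit wording would still remove doubt.

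**The sponsor.** A reader might infer that the sponsor is never told. The sponsor's identity is not visible in this copy, and the NHLBI Clinical Director may sit on the sponsor's side. Even so, that report waits for Continuing Review. Consent pages, the DSMB charter and NHLBI guidelines are also absent and could add something, so the point concerns the protocol text only.

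**The FDA link is modest.** The named fetal hazard is PET-CT radiation, whereas the IND product is Tubersol. The documents do not support a claim that an FDA duty would be breached.

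**Conclusion.** The point holds as a gap in ascertainment and timing. The protocol plans neither a prompt report of a pregnancy to the sponsor nor follow-up to outcome, so the birth-defect SAE it defines is reported only if the site learns of it after the woman has left the study.

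The size is small. With at most 25 enrolled, probably no or very few pregnancies will occur, and no endpoint or analysis changes. The day counts are illustrative: they rest on nominal visits and on assumed hCG lag, gestation and review interval, and should not be read as the protocol's own range. The finding itself does not depend on them. It is a cheap improvement worth making, because the protocol names both the hazard and the serious outcome.

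**What to change.** - **8.4.8:** report a pregnancy conceived before or during study exposure to the sponsor promptly once the site knows of it, and to the DSMB at its next review. Follow it, with the woman's consent, to outcome.
- **8.4.4:** state that a congenital anomaly in such a pregnancy is recorded and reported as an SAE whenever it is found.
- **Day 30 call:** add one question about pregnancy, and a reminder to report one found later, since a late conception may not yet test positive.

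The cost is minor protocol, CRF and consent-form wording, which needs IRB approval, plus follow-up contact for very few pregnancies. No visit or procedure is added.

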8.5 UNANTICIPATED PROBLEMS

8.5.1 Definition of Unanticipated Problems (UP)

Any incident, experience, or outcome that meets all of the following criteria:

- Unexpected in terms of nature, severity, or frequency given (a) the research procedures that are described in the protocol-related documents, such as the Institutional Review Board (IRB)-approved research protocol and informed consent document; and (b) the characteristics of the participant population being studied; and
- Related or possibly related to participation in the research (“possibly related” means there is a reasonable possibility that the incident, experience, or outcome may have been caused by the procedures involved in the research); and
- Suggests that the research places participants or others (which may include research staff, family members or other individuals not directly participating in the research) at a greater risk of harm (including physical, psychological, economic, or social harm) than was previously known or expected.

8.5.2 Unanticipated Problem Reporting

The investigator will report unanticipated problems (UPs) to the NIH Institutional Review Board (IRB) as per Policy 801.

8.5.3 NIH Intramural IRB Reporting of IND Safety Reports

Only IND Safety Reports that meet the definition of an unanticipated problem will need to be reported to the NIH Intramural IRB.

9 STATISTICAL CONSIDERATIONS

9.1 STATISTICAL HYPOTHESIS

- *Primary Endpoint:*
We hypothesize that antigen-specific CD4+ T cells response will be highest in the BAL five days post challenge in LTBI subjects alone and may subsequently wane 21 days post challenge.
- *Secondary Endpoint:*
We hypothesize that there will be significant FDG-avidity within the lung parenchyma and adjacent thoracic lymph node within the area of the lung (right upper lobe) in which PPD is selectively instilled. We expect that the SUV quantities will be most pronounced in LTBI subjects at day 4 post challenge and subsequently wane at day 20.
- *Exploratory Endpoints:*

We hypothesize that the phenotype and function of Mtb-specific T cells in the BAL will differ from that of circulating T cells. We hypothesize that bronchoscopic instillation of PPD will induce production of TH1 predominant pro-inflammatory cytokines, eicosanoid lipid mediators and defensins in the local airway environment more so than the systemic vasculature. We hypothesize that these soluble mediators will be primarily present in LTBI subjects on day 5 post challenge and wane at day 20.

9.2 SAMPLE SIZE DETERMINATION

This is a pilot study which will be hypothesis-generating in nature. For this reason we will not be pursuing the formal sample size calculation that corresponds to a specified statistical power. However, the sample size of 13 confirmed LTBI cases and 7 confirmed non-LTBI controls (a total of 20 subjects) is slightly larger than those of the original studies of the current bronchoscopic instillation model pioneered by Silver and colleagues (21-23). Silver's 2003, 2005 and 2011 PPD bronchoscopic instillation studies included a total of 9, 15, and 14 total subjects respectively. Each study was able to demonstrate a statistically significant increase in the frequency of Mtb-specific CD4+ T cells in the BAL of LTBI subjects as compared to the BAL of non-LTBI controls within each study. Furthermore, we anticipate that our immunological signals will likely stand out due to confirmation of LTBI status using concordant TST and IGRA testing. We will enroll up to an additional 5 subjects in order to achieve 20 completed studies.

9.3 POPULATIONS FOR ANALYSES

Not applicable.

9.3.1 Evaluable for toxicity

Not applicable.

9.3.2 Evaluable for objective response

Not applicable.

9.3.3 Evaluable Non-Target Disease Response

Not applicable

9.4 STATISTICAL ANALYSES

9.4.1 General Approach

Statistical analysis will be performed in R version 3.6.1 or later (CRAN.R-Project.org). For the analysis of primary and secondary endpoints, mixed effects models with repeated measure will be used to compare the LTBI and non-LTBI responses after bronchoscopic PPD instillation. For the primary hypothesis, the cell count for Mtb antigen-specific CD4+ and CD8+ T cells will be used as the response variable. Two separate statistical models will be entertained to explain the local pulmonary response and systemic vasculature, respectively. To guard against non-normal responses, a suitable data transformation on the response variable, e.g., log transform, will be performed if the original scale is highly skewed.

In regard to PET CT analysis, calculations for standardized uptake value will be made and normalized for scan differences using OsiriX MD (11). For the secondary hypothesis, the FDG SUV values from the PET CT image, measured at days -7, +4, and +20 days will be used as response in similar mixed effects models to study the group difference in average immunologic responses.

For the exploratory hypotheses, both numerical and graphical summary tools will be used to study the phenotypic and functional analysis of immune cell populations in the airways and circulation of individuals with or without LTBI. Also, descriptive statistics will be used to characterize the production of soluble mediators in BAL fluid and blood.

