1.3 SCHEDULE OF ACTIVITIES (SOA)

Schedule of Activities (SOA) AND ASSESSMENTS	EVALUATION	Screen*	Baseline						Study Visits 3 to 6			Telephone Follow- up Day 30
PROTOCOL TIMEPOINT			V1	V2	V3	V4**		V5	V6**			
Window +/- days	-60 Days	-7 Days			-2 /+3 D				-5 /+6D			
day /month				D0	D4	D5	D20	D21				
Assessments												
Review Inclusion/Exclusion Criteria	X											
Consent to study	X											
Review Medical History with Mtb Exposure		X ¹										
Review of Medications	X	X	X	X	X	X	X	X	X			
Physical Examination	X	X	X	X	X	X	X	X	X			
Weight, Height, and BMI	X											
Vital Signs (BP, HR, Resp, Temp O ₂ Saturation)	X	X	X			X			X			
Adverse Event Review			X	X	X	X	X	X	X		X	
CHEMISTRY LABS												
Female, Pregnancy Test (blood or urine) ²	X	X	X	X	X	X	X	X	X			
Acute Care Panel	X	X		X					X			
Mineral Panel	X	X		X				X			X	
CRP	X	X		X			X		X			
Hepatic Panel	X	X			X			X				
LDH	X	X		X			X		X			
International Normalized Ratio (INR), Prothrombin Time (PT), and Partial Thromboplastin Time PTT		X ³	X ³		X ³			X ³				
COVID-19 (PCR)	X											
HEMATOLOGY LABS												
CBC with differential	X	X		X			X		X			
ESR	X	X		X			X		X			
Viral Serologies												
Hepatitis B, C	X											
HIV	X											
Additional Tests												
*QuantiFERON Gold Test (IGRA)	X									X		
*Tuberculin skin test (TST)	X ⁴											
EVALUATIONS												
EKG	X		X		X			X		X		
*Chest X-RAY	X											
Chest PET-CT			X		X			X				
PROCEDURES												
Bronchoscopy					X ³			X ³		X ³		

STUDY MEDICATION							
Installation of Tuberculin Purified Protein Derivative (PPD) and saline			X				
Removal of Tuberculin Purified Protein Derivative (PPD) and saline cells				X		X	
Research Samples							
Immunology Assays = 40 mL via heparinized green top tubes			X	X		X	

* = Medical history screening activities may be done utilizing the Telehealth Visit Platform. Screening tests may be used as baseline if performed within 60 days. If re-screened after 60 days, the TST, IGRA, & chest x-ray will not be repeated unless there is a known tuberculosis exposure, including but not limited to travel to an endemic area or direct contact with an individual with known or suspected tuberculosis disease.

x¹ = History of exposure to persons with active TB; History of residence in a TB-endemic country and Estimate of time when LTBI most likely occurred

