4 STUDY DESIGN

4.1 OVERALL DESIGN

Hypothesis

The major hypothesis of this single-site pilot study is that recruitment of antigen-specific T cells and innate immune cell subsets following bronchoscopic instillation of purified protein derivative (PPD) from *M. tuberculosis* into the lung will occur primarily in individuals with latent TB infection. These Mtb-specific T cell responses will occur only in the segments into which PPD was instilled and not in the control lung segments. Lastly, pulmonary immune cell activation and number will peak early after PPD instillation and subsequently wane both in the airways and peripheral blood. These responses will be much more pronounced in the local pulmonary micro-environment as opposed to the systemic vasculature.

Using PET-CT imaging after PPD instillation, we hypothesize that it will be possible to identify increased cellular activity in draining thoracic lymph nodes, as well as in the pulmonary parenchyma. Furthermore, we expect that the above signals we are able to discern will progressively wane in the weeks following bronchoscopic PPD instillation.

Longitudinal Study Design

We plan to screen up to 100 non-LTBI controls vs confirmed LTBI to enroll up to 25 individuals in order to have a total of 20 individuals who are concordant on the PPD and IGRA test complete the study as follows:

Group A (LTBI Group): 13 PPD + and IGRA + subjects

[figure not shown]
Group B (non-LTBI Group): 7 PPD - and IGRA - subjects

We seek to enroll individuals at a 2:1 ratio of Group A:Group B in order to maximize the data derived from individuals with latent TB who will mount antigen-specific T cell responses post PPD instillation. This strategy will also decrease variance in Group A via relative oversampling compared to Group B.

Figure 1 outlines the experimental timeline. A baseline PET-CT study of the thoracic cavity will be obtained, and the first bronchoscopy will be performed in the following the week to collect the baseline BAL sample and to instill the PPD as outlined above. Peripheral blood will be collected at the time of each bronchoscopy procedure before the BAL. To examine early immune responses, on approximately day 4 the second PET-CT study will be obtained and the following day a second BAL will be performed, and peripheral blood samples will be collected. BAL will be done first in the control anterior segment of the left upper lobe and then again in the

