8.2 EFFICACY ASSESSMENTS

8.2.1 Clinical Evaluations

Physical examination

History and physical examination with vital signs (weight, height, BMI, blood pressure, respirations, heart rate, temperature and oxygen saturation) will be performed at screening with focus on respiratory and cardiovascular systems. Repeat physical examinations with focus on respiratory and cardiovascular systems with vital sign measurements (blood pressure, respirations, heart rate, temperature and oxygen saturation) will be performed prior to each bronchoscopy.

Radiographic or other imaging assessments.

Chest PET-CT Scan

Subjects will undergo a total of 3 PET/CT scans. A baseline PET/CT of the chest will be performed no more than one week prior to the initial bronchoscopy (10). In order to examine early immune responses, on day 4 post instillation bronchoscopy, a second PET-CT scan will be obtained. Furthermore, in order to examine the persistence of immune cell metabolic activity in the pulmonary parenchyma and thoracic lymph nodes, a PET-CT image will be obtained on approximately day 20 post initial bronchoscopic challenge.

Each participant will be asked to provide an estimate of their radiation exposure within the calendar in order to assess if participation in the study will cause a participant to exceed his/her annual dose limit.

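### Section 9.4.1 leaves the SUV scaling unstated and targets average SUV over all three scans, so a body-composition difference between the unmatched groups could enter the PET group contrast

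*Combined protocol and SAP*

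**What the plan says.** Section 9.4.1 describes the SUV calculation in one clause: "calculations for standardized uptake value will be made and normalized for scan differences using OsiriX MD". It does not say whether SUV is scaled to body weight, lean mass, surface area or a reference tissue. The SUV values "measured at days -7, +4, and +20 days will be used as response in similar mixed effects models" are to be used "to study the group difference in average immunologic responses". The day -7 scan precedes the PPD challenge, yet it is listed as a response alongside the two later scans. No group-by-time term, baseline adjustment or body-size covariate is named.

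The groups are defined by concordant TST and IGRA results, not by randomisation, and no matching is described. Section 4.1 states: "We seek to enroll individuals at a 2:1 ratio of Group A:Group B"; the targets are 13 LTBI and 7 non-LTBI. Both sexes aged 18 to 64 may enter, and Section 5.2 excludes on BMI only above 40. Body size is recorded: Section 1.3 lists "Weight, Height, and BMI", and Section 8.2.1 says "vital signs (weight, height, BMI, blood pressure, respirations, heart rate, temperature and oxygen saturation) will be performed at screening". Age is the only patient factor named for the endpoint analyses (Section 9.4.6). Section 9.4.4 plans a descriptive comparison of baseline demographics by group.

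The hypothesis in Section 9.1 is narrower than the modelling target. It expects uptake in the region of the right upper lobe, most marked in LTBI participants at day 4 and waning by day 20.

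**The concern.** In its common form, SUV divides tissue activity by injected dose per kilogram of body weight. If fat takes up little FDG but counts in the weight, a person with more fat shows a higher SUV in lung or node for the same tissue uptake. That is a multiplier attached to the person, present equally at all three scans. Correcting for differences between scans need not remove it.

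A contrast in average SUV between two unmatched groups keeps such a multiplier. If LTBI and non-LTBI volunteers differ systematically in body fat or sex mix, part of the group effect would be body composition read as immune activity. If they do not differ systematically, the multiplier still widens the between-person spread, which matters with 13 against 7.

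**Working it through.** The plan has no figure to reproduce. Section 9.2 says "we will not be pursuing the formal sample size calculation that corresponds to a specified statistical power", and no alpha or SUV variability is given. A two-sided 5% level is used below only as a yardstick.

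**Inputs from the documents:** 13 and 7 participants; scans at days -7, +4 and +20.

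**Assumptions:** SUV is scaled to body weight. Fat takes up a fraction k of the lean-tissue concentration, with k = 0.2 and a range of 0 to 0.4. The SD of fat fraction f is 0.08, around a mean of 0.28. Log SUV has between-person SD 0.15 and, where three scans are modelled, within-person SD 0.15. There is no true group difference.

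**1. Multiplier for one person.** Lean-tissue SUV is multiplied by 1/(1 - (1 - k)f). At k = 0.2 this is 1/(1 - 0.16) = 1.190 for f = 0.20 and 1/(1 - 0.32) = 1.471 for f = 0.40, a ratio of 1.235. For k = 0 the ratio is 1.333 and for k = 0.4 it is 1.158. These ratios compare two individuals, not two group means.

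**2. Shift in the group contrast.** On the log scale the slope in f is (1 - k)/(1 - (1 - k)f) = 0.8/0.776 = 1.031 at f = 0.28. Mean gaps of 0.05, 0.08 and 0.10 shift the contrast by about 0.052, 0.082 and 0.103.

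**3. Added noise.** The standard error multiplier is √(1/13 + 1/7) = 0.469. The factor contributes an SD of 1.031 × 0.08 = 0.0825.
- One value per person: 0.15 × 0.469 = 0.070 without the factor; √(0.15² + 0.0825²) × 0.469 = 0.080 with it. The increase is 13% to 15%, depending on rounding and simulation error.
- Three-scan average: √(0.0225 + 0.0225/3) × 0.469 = 0.081 without; √(0.0225 + 0.0075 + 0.0068) × 0.469 = 0.090 with, about 11% larger.

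**4. False positives (simulated, two-sample t test on per-person summaries, k = 0.2).**

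| Mean fat-fraction gap | One SUV per person | Average of three scans | Lean-scaled SUV, or log change from day -7 |
|---|---|---|---|
| 0 | 5% | 5% | about 5% |
| 0.05 | 9–10% | 8–9% | about 5% |
| 0.08 | 16–17% | about 14% | about 5% |
| 0.10 | 23–24% | about 20% | about 5% |

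An upper-bound version (k = 0, fat-fraction SD 0.07, average of three scans) gives about 11% for mean fat shares of 25% versus 30%, and 31% for 25% versus 35%. Lean-scaled SUV and log change again stay near 5%. Change on the raw scale cancels the multiplier only partly: 5% to 8% up to 25% versus 35%.

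**5. Chance imbalance.** With no systematic gap, the standard error of the fat-fraction difference is 0.469 × 0.07 to 0.08 = 0.033 to 0.038. A chance gap above 0.05 in either direction then occurs in about 13% to 18% of such trials. This is already contained in the noise of step 3 and leaves the error rate at 5%.

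**6. Price of a change score.** The log change from day -7 to day 4 has standard error √2 × 0.15 × 0.469 = 0.099, against 0.090 for the three-scan average. If a group difference e at day 4 halves by day 20 and is zero at day -7, the three-scan average captures (0 + e + e/2)/3 = e/2, while the day 4 change captures e.

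**The case against.** The strongest reply is that the plan does not commit to the harmful analysis. Section 9.4.1 calls for repeated-measures models with a pre-challenge scan. Section 9.1 frames the question by region and over time, and Section 3 measures SUV across all lung fields. A constant multiplier cancels in a log change from day -7, or in a ratio of the challenged to the control side. The phrase about average responses could mean group means at each time. The normalisation clause also cites a method paper not reproduced in the documents, so it may do more than its wording says. This stands to the extent that the fault is an unspecified analysis with a vulnerable reading, not a stated error. It does not remove the point: Section 9.4.1 names neither contrast, and the log transform described there is conditional on skewness, whereas cancellation depends on the log scale.

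A reader might infer that the plan uses body-weight SUV and that its PET comparison is therefore biased by body fat. The documents do not support that. They never state body-weight scaling or the effect of fat on SUV, and they give no BMI by group, so the gaps of 0.05 to 0.10 are illustrations.

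It is also fair that the t test on per-person summaries only stands in for the mixed model, that no alpha is declared, and that the study is a pilot. These limit the severity.

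**Conclusion.** The point holds as a gap in specification with a plausible and avoidable consequence. As written, Section 9.4.1 leaves the SUV scaling open and includes the pre-challenge scan in an average contrast between unmatched groups. If SUV is scaled to body weight, if fat takes up less FDG than lean tissue, and if the groups differ systematically in body composition, that contrast is biased. The false-positive rate would be roughly 8% to 24% for fat-fraction gaps of 0.05 to 0.10 at k = 0.2, and higher at the k = 0 bound. If the third condition fails, the cost is only precision. Nothing in the documents shows that a systematic gap exists or which way it would run, so the reading that any group difference in SUV would be a body-fat artefact goes too far. Severity is minor to moderate: the endpoint is secondary and the study is hypothesis-generating.

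**What to change.** In Section 9.4.1:

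- Name the group-by-time contrast in log SUV change from day -7, to day 4 and to day 20, as the main PET comparison. This matches the hypothesis in Section 9.1 and cancels any constant per-person factor, whatever the scaling. Fix the log scale in advance instead of making it depend on skewness.
- State what SUV is scaled to.
- For any comparison of SUV levels between groups, use SUV scaled to lean body mass, computed from sex, height and weight as recorded, and keep body-weight SUV as a sensitivity analysis.
- Report BMI and sex by group within the baseline description already planned in Section 9.4.4.

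The cost is analysis wording only; no new measurement is needed. There are two downsides. A change score carries the noise of two scans (standard error 0.099 against 0.090 under the assumptions above). Lean mass predicted from a formula is less accurate at high BMI, which is why it supports the change contrast and does not replace it.
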